6.1 Study Endpoints

Primary Endpoints: The practice pattern survey completed during the first 8 months will provide the baseline data that will be compared to results obtained after implementation of the decision aid.

Secondary Endpoints: A total of five patient-reported instruments will be used to score overall and lung cancer-specific quality of life, decision-support preferences, decisional conflict, and satisfaction with decision:

Decision Support Preference Questionnaire (DMPQ)

FACT-L

FACT/NCCN-Lung Symptom Index (NCCN-FACT FLSI-17)

Decisional Conflict Scale (DCS)

Post-Consultation Questionnaire

Satisfaction with Health Care Decision (SWD).

6.1.1 Study Design

This study involves the evaluation of the decision support tool Patients with Power, previously used with breast cancer patients, in the non-small cell lung cancer patient population.

1. Characterize physician and patient populations and treatment decisions in the UCSF thoracic oncology practices.
2. Establish the acceptability, feasibility, and effectiveness of a novel decision aid for decisions made about treatment for NSCLC.
3. Conduct an evaluation of changes in NCCN-guided practice patterns before and after implementation of the decision aid, with respect to 6 clinical scenarios:

All patients: if smoking cessation intervention is provided at initial visit;

Stage IB-IIB patients receiving surgery: if adjuvant chemotherapy is given after surgery;

Stage III patients receiving surgery: if pathologic staging of mediastinal nodal disease is done prior to initiation of therapies;

Stage III patients not receiving surgery: if pathologic staging of mediastinal nodal disease is done prior to initiation of therapies;

Stage III patients not receiving surgery: if concurrent chemoradiation is given upfront;

Stage IV patients: if molecular testing is done prior to initiation of systemic therapy.

4. Collect data to facilitate the design of future larger-scale evaluations, including assessments of physician-patient agreement and patients' levels of decisional conflict and satisfaction with decisions made as well as potential correlations to patient-reported quality to life.

6.2 Determination of Sample Size and Accrual Rate

6.2.1 Sample Size and Power Estimate

We expect that the clinical volume of 30 patients/month for 12 months will yield a potential enrollment pool of 360 patients. Anticipating a 30% decline, dropout, or ineligibility rate at the time of potential enrollment, then at least 250 patients should be evaluable. The sample size was determined based on the primary outcomes of changes in practice patterns. For each disease stage, a test of at least a 25% improvement using the decision aid compared with the pre-intervention results in the proportion of patients satisfying the stage-specific criterion listed above will be carried out (see Primary Endpoint for practice pattern metrics). In addition, the entire study sample will be evaluated to test for a change in smoking cessation plans. Patients will be included in up to 3 individual analyses. The maximum sample size for any one test is based upon assuming a null hypothesis of 50% in the pre-intervention cohort. This estimate for the null hypothesis will be modified using the results obtained prior to use of the decision aid (Months 1-8). Based upon the one-sample binary exact test with power set at 90% and a 2-sided type I error of 0.017 (adjusted for up to 3 tests for all patients), 53 patients would be required for each test. The test would reflect the actual accrual by stage with the use of the decision aid. With a fixed type I error of 0.017, this means for any individual test that the sample size may differ from 53, and the null hypothesis may differ from 50% and result in reduced power but will be at least 80%. For example, if adjuvant chemotherapy is given after surgery to 40% of stage IB and II patients determined from the pre-intervention assessment, then a test to detect a 50% improvement to 60% will require 70 patients with 80% power and 88 patients with 91% power. Similarly, if 60% of patients satisfy the smoking cessation criterion during the

pre-intervention interval, a 50% improvement will require 32 patients with 92% power, but a 15% improvement with 90% power requires 135 patients across all disease stages. It is therefore not anticipated that the comparisons will require more than the expected enrollment of 250 patients.

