2.1 Primary

The primary study outcomes will emerge from measurement of changes in overall practice patterns after implementation of the decision aid. Pre- and post-intervention data will be used to determine the level of difference before and after implementation of the decision aid into the thoracic oncology clinics. Six specific practice patterns will be queried in a binary (yes/no) manner:

1. All stages: smoking cessation discussion reinforced with a specific followup plan and/or medication/patch/psychotherapy or counseling;
2. Stage IB, IIA, IIB receiving surgery: adjuvant chemotherapy given after surgery;
3. Stage III receiving surgery: pathologic staging of mediastinal nodal disease prior to initiation of therapies;
4. Stage III not receiving surgery: pathologic staging of mediastinal nodal disease prior to initiation of therapies
5. Stage III patients not receiving surgery: if concurrent chemoradiation is given upfront
6. Stage IV: molecular testing for EGFR and ALK mutations prior to initiation of systemic therapy.

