GE3	I am losing hope in the fight against my illness.....	0	1	2	3	4
GE4	I feel nervous.....	0	1	2	3	4
GE5	I worry about dying.....	0	1	2	3	4
GE6	I worry that my condition will get worse.....	0	1	2	3	4

FUNCTIONAL WELL-BEING

	Not at all	A little bit	Some- what	Quite a bit	Very much
--	---------------	-----------------	---------------	----------------	--------------

GF1	I am able to work (include work at home)	0	1	2	3	4
GF2	My work (include work at home) is fulfilling.....	0	1	2	3	4
GF3	I am able to enjoy life.....	0	1	2	3	4
GF4	I have accepted my illness.....	0	1	2	3	4
GF5	I am sleeping well	0	1	2	3	4
GF6	I am enjoying the things I usually do for fun	0	1	2	3	4
GF7	I am content with the quality of my life right now.....	0	1	2	3	4

FACT-L (Version 4)

Please circle or mark one number per line to indicate your response as it applies to the past 7 days.

ADDITIONAL CONCERNS		Not at all	A little bit	Some-what	Quite a bit	Very much
B1	I have been short of breath	0	1	2	3	4
C2	I am losing weight.....	0	1	2	3	4
L1	My thinking is clear	0	1	2	3	4
L2	I have been coughing	0	1	2	3	4
B5	I am bothered by hair loss	0	1	2	3	4
C6	I have a good appetite	0	1	2	3	4
L3	I feel tightness in my chest.....	0	1	2	3	4
L4	Breathing is easy for me	0	1	2	3	4
Q3	Have you ever smoked? No ____ Yes ____ If yes:					
L5	I regret my smoking	0	1	2	3	4

Decisional Conflict Scale (DCS)

	Strongly Agree	Agree	Neither Agree Nor Disagree	Disagree	Strongly Disagree
I know which options are available to me.					
I know the benefits of each option.					
I know the risks and side effects of each option.					
I am clear about which benefits matter most to me.					
I am clear about which risks and side effects matter most to me.					

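### Metric 1 (smoking cessation) is scored yes/no in all patients although it does not apply to non-smokers, so a gain among smokers is diluted and the test responds to the smoker mix

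*Combined protocol and SAP*

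**What the plan says.** Section 2.1 introduces the primary outcome with "Six specific practice patterns will be queried in a binary (yes/no) manner". The first pattern reads "All stages: smoking cessation discussion reinforced with a specific followup plan and/or medication/patch/psychotherapy or counseling". Section 6.1.1 gives its population as "All patients: if smoking cessation intervention is provided at initial visit", and section 6.2.1 adds that "the entire study sample will be evaluated to test for a change in smoking cessation plans". The worked example in 6.2.1 also counts patients, not smokers: it supposes what happens "if 60% of patients satisfy the smoking cessation criterion" before the intervention, and concludes that "a 15% improvement with 90% power requires 135 patients across all disease stages".

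The other five metrics are each limited by stage, and four of them also by whether surgery is received. Metric 1 has no such limit. Smoking status does not appear in the eligibility criteria (3.2.1, 3.2.2), and no section gives a not-applicable code or a scoring rule for non-smokers.

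The test is a one-sample exact binomial test at two-sided 0.017. Its planning null of 50% is to be replaced by what is seen in Months 1-8. Section 6.3.1 adds logistic regression as a more detailed analysis, with nodes, tumour size and histology as its example covariates.

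**The concern.** A cessation plan can be given only to someone who smokes. With all patients in the denominator, every non-smoker carries a fixed score that the decision aid cannot change. Two things follow.

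- **Dilution.** A real improvement in the counselling of smokers appears in the all-patient rate only in proportion to the smoker share. It can be missed if smokers are a minority.
- **Sensitivity to mix.** The test compares the post-implementation rate with a fixed pre-implementation rate, unadjusted. If the smoker share differs between periods, the rate moves even when counselling does not.

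This is the one primary test planned for the whole sample, and it is the metric for which 6.2.1 works through a 15-point gain.

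**Working it through.** **Inputs from the documents.** Enrolment 250 (3.1); exact one-sample test, two-sided 0.017, taken here as 0.0085 per tail; smoking example with 60% at baseline; base case with a 50% null and a 25% improvement (all 6.2.1).

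**Assumed.** The smoker share s, and any shift in it, because the documents give neither. The baseline rate is treated as known, as the plan does, except in step 5.

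**1. The plan's own figures.**
- 60% to 75%, n=135: reject at 95 or more, power 90.8% (stated 90%).
- 50% to 75%, n=53: reject at 36 or more, power 90.8% (stated 90%).
- 60% to 90%, n=32: power 90.6% (stated 92%).

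The improvements are therefore percentage points. Read as relative, 15% would be 60% to 69%, with power of only 40.5% at n=135. These figures hold for rates over whichever patients are counted.

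**2. Dilution.** Let r be the rate among smokers.
- *No* scoring: all-patient rate = r·s.
- *Yes* scoring: all-patient rate = r·s + (1 − s).

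In both cases a change Δ among smokers becomes s·Δ. At s = 40% and r from 60% to 75%:
- *No*: 0.24 to 0.30, reject at 77 or more of 250, power 41%.
- *Yes*: 0.84 to 0.90, reject at 224 or more of 250, power 63%.
- Smokers only: n = 100, reject at 72 or more, power 79%.

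| Smoker share (assumed) | 60% to 75%: no / yes / smokers only | 50% to 75%: no / yes / smokers only |
|---|---|---|
| 20% | 14% / 19% / 38% | 49% / 63% / 90% |
| 30% | 26% / 39% / 59% | 76% / 91% / 98% |
| 40% | 41% / 63% / 79% | 88% / 97% / over 99% |
| 50% | 51% / 74% / 86% | 97% / over 99% / over 99% |
| 60% | 69% / 86% / 93% | 99% / over 99% / over 99% |
| 80% | 91% / 97% / 98% | over 99% in all three |

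For 60% to 90%, among shares of 20% or more, only *no* scoring at about 20-25% smokers falls below 80% (59% and 76%). Under *no* scoring the all-patient rate cannot exceed s, so the plan's example of 60% of patients rising to 75% would need at least 75% smokers.

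**3. Shift in mix.** Counselling is held at 60% of smokers, n=250. The figure is the chance of a false improvement, nominally at most 0.85%.

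| Scoring | Share, pre to post (assumed) | All-patient rate | False improvement |
|---|---|---|---|
| no | 30% to 35% | 0.18 to 0.21 | 11% |
| no | 60% to 65% | 0.36 to 0.39 | 8% |
| yes | 35% to 30% | 0.86 to 0.88 | 7% |
| yes | 65% to 60% | 0.74 to 0.76 | 4% |
| no | 30% to 32% | 0.180 to 0.192 | 2.5% |
| yes | 32% to 30% | 0.872 to 0.880 | 1.6% |

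The opposite shift hides a real gain. With *no* scoring, a share falling from 35% to 30% and a true rise from 60% to 75%, the all-patient rate goes from 0.21 to 0.225. Power is 3%, against 59% in the 75 smokers alone.

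**4. Smokers needed.** For 60% to 75%, power first reaches 80% at 103 smokers and stays there from 112; the exact test is not smooth in between. 103/250 = 41% and 112/250 = 45%. The plan's 135-patient example needs 135/250 = 54% smokers.

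**5. What a smokers-only test leaves open.** With a known baseline and no change, its two-sided error is about 1.3-1.5%. If the null is an estimate from an assumed 240 baseline patients (30 a month for 8 months), it is about 8-9%. With an assumed 120 it is about 16%.

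**The case against.** **The wording may mean less than it says.** In 2.1 the label can be read as not restricted by stage, and a cessation discussion presupposes a smoker, so chart reviewers might leave non-smokers out. That reading is possible, but 6.1.1 and 6.2.1 name all patients and the entire sample, and the example counts patients. An unwritten exclusion could also be applied differently in the two periods.

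**The plan adjusts.** Logistic regression stands under the Primary Analysis heading in 6.3.1, and its covariate list is only illustrative, so smoking status could enter. It is described as further analysis, does not name smoking status and does not replace the exact test.

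**The null is reset from Months 1-8.** This fits the null to the baseline mix. It cures neither dilution nor a later change in mix.

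**The shares and shifts are hypothetical.** This stands. The baseline comes from chart review and observed visits, while the later cohort is consenting patients able to use a web interface. A difference in mix is therefore possible, but no direction or size is documented, and a 2-point shift does little harm.

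Three stronger readings are tempting and not supported:
- That the FACT-L item "Have you ever smoked" shows that the planners expected never-smokers. It is a fixed item in a reused instrument. It records ever-smoking, only in enrolled patients, and says nothing about the expected mix or the baseline cohort.
- That the test is underpowered in general. For 50% to 75%, all-patient power is 88% or more from a 40% share upward.
- That testing smokers only brings the error to its nominal level. Step 5 shows that this holds only if the baseline rate is treated as known.

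**Conclusion.** The concern holds as a flaw in the stated denominator, not only as missing detail: under either scoring of non-smokers, the all-patient rate dilutes a gain among smokers and ties the result to the smoker share. The size cannot be fixed from the documents. It is serious for a 15-point gain when smokers are a minority and small for a 25-point gain when 40% or more smoke. The false-improvement figures are conditional on assumed shifts and on a baseline rate taken as known. The documents do not show that a shift will occur, nor how non-smokers would be scored. The point should be corrected, but it does not invalidate the other five metrics.

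**What to change.** In 2.1, 6.1.1 and 6.2.1, and where the abstract and 1.3 repeat the metric:

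- Define the metric 1 denominator as patients documented in the chart as current smokers at the initial visit. The investigators state whether recent quitters count.
- Code all other patients not applicable.
- Apply the same rule in both periods, and fix it in writing before the Months 1-8 baseline is scored.
- Restate power for the expected number of smokers, using the 103-112 and 135 figures above as reference points.
- Report the all-patient rate and the smoker share in each period descriptively.

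**Cost.** Wording changes and one chart field in both periods. The test sample is smaller. If smokers are under about 41-45% of 250, the plan must state less than 80% power for 60% to 75%, or a larger detectable change. Where most patients smoke, little power is gained and the main benefit is protection from a change in mix.

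**Not covered.** The change removes dilution and the effect of smoker mix. The error from using an estimated Months 1-8 rate as a fixed null is separate and remains.

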Duration of study	
Twenty four months:
 
Month 1-8: (1) Analyze existing practice patterns focused on 6 decision nodes derived from the NCCN decision tree for NSCLC. The study of practice patterns will be based on primarily on review of medical records by a trained research coordinator under [name] direction. (2) Programming of NSCLC decision aid under [name] direction, conducted with technical assistance as needed from PwP. The results will be reviewed by co-investigators for accuracy and ease of use.
 
Month 8-20: Conduct prospective trial of the decision aid, collecting data directly from patients over the course of their initial 2 consultations.
 
Month 20-24: Completion of data collection and data analysis activities.

Study Intervention	The interactive PwP interface allows structured exploration of choices, sequencing, and timing of therapies. The aid thus enables the patient to discuss proposed treatments with the oncologist (rather than assuming passive acceptance). Furthermore, the decision aid allows evolving display of the treatment choices and timeline/calendar in a graphical, simplified format during the discussion (rather than assuming absorption and recall of details of a verbal communication). We will collect pilot data related to the collaborative, patient-oriented approach facilitated by this decision aid.
Study Assessments	
A total of five patient-reported instruments will be used to score overall and lung cancer-specific quality of life, decision-support preferences, decisional conflict, and satisfaction with decision:
 
 1. Decision Support Preference Questionnaire (DMPQ) 2. FACT-L 3. FACT/NCCN-Lung Symptom Index (NCCN-FACT FLSI-17) 4. Decisional Conflict Scale (DCS) 5. Post-Consultation Questionnaire 6. Satisfaction with Health Care Decision (SWD)

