1.3 Rationale for the Proposed Study

This is a two-year career development project to develop and field-test a decision aid based on the NCCN patient guidelines for NSCLC. The study goal is to improve the treatment decision-support process in NSCLC patients in an academic medical center. If successful, this decision aid will be disseminated more broadly to community settings.

This study will consist of a development phase followed by an evaluation phase. After initial prototyping, refinement, coding, and implementation of the intervention, a study will be implemented using a pre/post design to estimate the effect size of the intervention with respect to disseminating NCCN-guided treatment choices (primary outcome) and to generate preliminary data about secondary outcomes.

Specifically, this project will:

1. Characterize physician and patient populations and treatment decisions in the UCSF thoracic oncology practices.
2. Establish the acceptability, feasibility, and effectiveness of a novel decision aid for decisions made about treatment for NSCLC.

3. Conduct an evaluation of changes in NCCN-guided practice patterns before and after implementation of the decision aid, with respect to 6 clinical scenarios:

1. All patients: if smoking cessation intervention is provided at initial visit;
2. Stage IB-IIB patients receiving surgery: if adjuvant chemotherapy is given after surgery;
3. Stage III patients receiving surgery: if pathologic staging of mediastinal nodal disease is done prior to initiation of therapies;
4. Stage III patients not receiving surgery: if pathologic staging of mediastinal nodal disease is done prior to initiation of therapies
5. Stage III patients not receiving surgery: if concurrent chemoradiation is given upfront;
6. Stage IV patients: if molecular testing is done prior to initiation of systemic therapy.

4. Collect data to facilitate the design of future larger-scale evaluations, including assessments of physician-patient agreement and patients' levels of decisional conflict and satisfaction with decisions made.

2 Objectives of the Study

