6.3 Analyses Plans

6.3.1 Primary Analysis (or Analysis of Primary Endpoints)

The major focus of the trial analysis will be to determine if there is a statistically discernible effect for the decision aid in influencing practice patterns before and after implementation of the decision aid. The rates of NCCN adherence by stage will be an important covariate. The current sample size now reflects the ability to detect a moderate effect size for decision aid interactions with outcomes. More detailed analysis to correlate correlations between changes in practice patterns to other variables will be carried out with logistic regression, with special modifications for patient sociodemographic and clinical characteristics (e.g., nodes, tumor size, histology).

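### Section 6.2.1 tests each practice pattern against the observed months 1-8 rate as if it were a known constant, so neither the 0.017 error rate nor the stated power holds

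*Combined protocol and SAP*

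**What the plan says.** Three places describe a comparison of two samples. Section 1.3 describes a study "using a pre/post design to estimate the effect size of the intervention". Section 6.1 says "The practice pattern survey completed during the first 8 months will provide the baseline data that will be compared to results obtained after implementation". Section 6.3.1 sets out to "determine if there is a statistically discernible effect for the decision aid in influencing practice patterns before and after implementation of the decision aid".

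Section 6.2.1 commits to carrying out, for each disease stage, "a test of at least a 25% improvement using the decision aid compared with the pre-intervention results". The sample size is "Based upon the one-sample binary exact test with power set at 90% and a 2-sided type I error of 0.017", the 0.017 being an adjustment for up to three tests per patient. With a planning null of 50%, this gives 53 patients per test. On that null it adds: "This estimate for the null hypothesis will be modified using the results obtained prior to use of the decision aid (Months 1-8"). The type I error stays at 0.017 when the null changes. Departures from 53 patients or from a 50% null may, it says, "result in reduced power but will be at least 80" percent.

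No section says how many baseline patients or records there will be, overall or per metric, or how far back they reach. The source is described in two ways. The abstract (Duration of study) says "The study of practice patterns will be based on primarily on review of medical records"; section 3.5 says direct observation of new visits together with record review. Section 6.3.1 names no test for the before/after comparison. It mentions logistic regression for further analysis relating changes to other variables. Chi-square appears once, in 6.3.2, under the secondary analyses.

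**The concern.** A one-sample exact test is valid when the reference rate is fixed in advance. Here it is a proportion observed in a finite group of earlier patients. If practice does not change, the baseline rate will still be too high or too low by chance, and the test reads that error as an effect of the decision aid. The false-positive rate then depends on the baseline size, which the plan leaves open.

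This affects all six primary metrics, and the smoking metric most, because it uses the whole post sample. It undoes the plan's own multiplicity adjustment (0.05/3 = 0.017). A false claim of improved guideline adherence would matter, since section 1.3 links success to wider dissemination. The estimation aim is affected too: an interval for a before/after difference needs the variance of both rates.

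**Working it through.** **Inputs.** From 6.2.1: two-sided 0.017; 53 post patients for 50% to 75%; 70 and 88 for 40% to 60%; 135 for a 15% improvement from 60%; 32 for 60% to 90%; 30 patients a month; a 30% loss; 250 enrolled. Baseline counts are assumptions. For illustration: 240 = 30 x 8 months; 168 = 240 x 0.7; 35 = 53 x 8/12 (likewise 47, 59 and 90 for 70, 88 and 135); and one to three times the post sample.

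**Step 1: the plan's figures.** Exact binomial test, each tail at most 0.0085, null treated as known. For n = 53 and p0 = 0.50, reject at 17 or fewer or 36 or more. The attained size is 0.0127 and power at 0.75 is 90.8%. Similarly, 40% to 60% gives 80.4% (n = 70) and 91.4% (n = 88); 60% to 75% with n = 135 gives 90.8%; 60% to 90% with n = 32 gives 90.6% (92% stated). So the figures rest on a known null. The 53 and the 135 reproduce only if improvement means percentage points: 50% to 62.5% with 53 patients has 25% power.

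**Step 2: type I error with an estimated null.** For baseline X ~ Bin(m, p) and post Y ~ Bin(n, p) with the same p, take exact critical values for Bin(n, X/m) and sum the rejection probability over X.

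| Post n | True rate | Baseline m: type I error |
|---|---|---|
| 53 | 50% | 35: 11.8%; 53: 7.0%; 106: 3.8%; 240: 2.3%; 460-480: 1.7%; 500: 1.6% |
| 250 | 50% | 168: 12.5%; 240: 8.7%; 500: 4.7% |
| 250 | 60% | 168: 12.2%; 240: 8.9%; 500: 4.6% |

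False improvement is about half of each figure. A large-sample check explains the pattern. The test uses variance p(1-p)/n where the true variance is p(1-p)(1/n + 1/m), so the error is about 2[1 - Phi(2.387/sqrt(1 + n/m))]. For n = m this is 2[1 - Phi(1.688)] = 9.1%. The exact 7.0% is lower because the exact test is conservative (0.0127), which offsets only part of the inflation. Over true rates of 40% to 90%, the baseline must be about 6 to 9 times the post sample for n = 53, and 12 to 20 times for n = 250, before the error is back to 0.017.

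**Step 3: power of the plan's test with an estimated null.**

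| Scenario | Stated | Baseline m: power |
|---|---|---|
| 50% to 75%, 53 post | 90% | 35: 79%; 53: 81%; 106: 84%; 240: 88%; 500: 89% |
| 40% to 60%, 70 post | 80% | 47: 71%; 70: 73%; 140: 77%; 210: 77% |
| 40% to 60%, 88 post | 91% | 59: 80%; 88: 83%; 176: 85%; 264: 87% |
| 60% to 75%, 135 post | 90% | 90: 78%; 135: 81%; 168: 82%; 240: 84% |
| 60% to 90%, 32 post | 92% | 20: 80%; 32: 84%; 48: 87%; 100: 90%; 240: 92% |

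For smoking, 60% to 75% with 250 post, power is 95% to 97% at 168 to 240 baseline. All these figures are flattered by the inflated error in step 2.

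**Step 4: power of a two-sample test at 0.017** (pooled chi-square, full enumeration).

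| Scenario | Baseline m: power |
|---|---|
| 50% to 75%, 53 post | 35: 53%; 53: 62%; 106: 76%; 150: 81%; 240: 85% |
| 40% to 60%, 70 post | 47: 39%; 70: 48%; 140: 64%; 210: 71% |
| 40% to 60%, 88 post | 59: 51%; 88: 63%; 176: 75%; 264: 82% |
| 60% to 75%, 250 post | 168: 80%; 240: 88% |

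For 90% power at 50% versus 75% with equal periods: [2.387 x sqrt(2 x 0.625 x 0.375) + 1.282 x sqrt(0.25 + 0.1875)]^2 / 0.25^2 = (1.634 + 0.848)^2 / 0.0625, or 99 per period.

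**The case against.** The one-sample test is named only in the sample-size section, so it could be a planning device. The paragraph in 6.3.2 that lists chi-square opens by referring to all data analyses and ranks effect sizes and 95% intervals above p-values. A reader could extend it to the primary metrics, and a two-sample analysis is not ruled out. But 6.2.1 says the tests will be carried out, with the null updated and the error rate held, and no section names another primary test. If the test was only for planning, the sizing is still wrong for the comparison intended: 62% power at 53 against 53.

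Record review could supply a large baseline, and at 240 in a stratum the error is only 2.3%. That stands, but 240 must be the count for that metric. If 53 of 250 post patients fall in a stratum (21.2%) and the stage mix is the same, 240 baseline patients there imply about 240/0.212 = 1,130 in all, or 38 months at 30 a month. The 12% end of the smoking range applies the enrolment loss to a chart-based baseline; without it the figure is about 9%.

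The 80% floor is not generally broken. Step 3 shows it met for 88 and 32 post patients at every baseline tried, for 53 and 135 once the baseline equals the post sample, and for smoking at 250. Only the 70-patient case, sized at 80% to begin with, misses it throughout. The floor is therefore unsupported as a guarantee, not impossible.

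Finally, this is a pilot meant partly to estimate an effect. That lowers the weight on the p-value, but 6.2.1 and 6.3.1 still commit to formal testing.

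**Conclusion.** The plan is wrong as written on this point, and it should be corrected before the primary analysis. With the observed baseline rate used as a fixed null, the type I error exceeds 0.017 unless that metric's baseline is several times its post sample: about nine times for 53 patients at a true rate of 50%, and 12 to 20 times for 250. At a baseline equal to the post sample, it is about four times nominal (7.0% against 1.7%). The stated 90% power at 53 patients is not reached at any baseline in step 3, and under a valid two-sample test about 150 baseline patients in the stratum are needed even for 80%.

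The sizes depend on assumed baseline counts, and the power figures for 53 and 135 patients on reading improvement as percentage points. The type I error does not depend on that reading. The two descriptions of the baseline source are a lesser point, but they must be reconciled before any count can be stated.

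**What to change.** In 6.2.1 and 6.3.1, make the primary analysis of each metric a two-sample comparison of the baseline and post-implementation cohorts, using patient-level outcomes. An unadjusted chi-square or Fisher test, with the difference in proportions and its confidence interval, should be the core. Logistic regression with a period term and the covariates listed in 6.3.1 can support it where numbers allow, but may be unstable in the small stage III strata.

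State the baseline count, calendar period and source for each metric, reconciling the abstract with section 3.5. Say whether improvement is absolute or relative. Replace the 53-patient, 90% and 80%-floor statements and the worked examples with two-sample power at the actual baseline and expected post counts.

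The cost is protocol wording, a less favourable power statement for the stage-specific tests, and keeping baseline outcomes per patient, not only as a rate. No extra prospective patients are needed if the restated power is accepted. A larger record-review baseline would recover some of the power.

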6.3.2 Secondary Analysis (or Analysis of Secondary Endpoints)

In addition to the primary analysis, additional analyses will be carried out to determine correlations between sociodemographic and clinical variables, similarity in physician and patient post-consultation reports, quality of life scores, decision-support preferences, decisional conflict, and satisfaction with decision.

All data analyses will be conducted by first using exploratory data techniques to examine univariate and bivariate relationships for statistical significance. Multivariate models will be constructed using statistical criteria, plausibility of associations, the existence of a priori hypotheses, and proposed causal pathways. Chi-square, non-parametric and log-linear techniques will be used for categorical or ordinal data, and t-tests, where appropriate, for continuous data. Multivariate models will use the observed likelihood ratio statistic as a statistical index of model fit. Observed effect sizes and their precision (expressed as 95% confidence intervals) will be more important components of these analyses than the associated p-values.

7 Study Management

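### Does testing six primary practice patterns at 0.017 each, with no rule for overall success, leave the error rate uncontrolled?

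*Combined protocol and SAP*

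**What the plan says.** Section 2.1 bases the primary outcomes on "measurement of changes in overall practice patterns after implementation of the decision aid" and lists six yes/no patterns. Section 6.1.1 repeats that practice is compared before and after the aid "with respect to 6 clinical scenarios". One pattern (smoking cessation) applies to the whole sample. The other five belong to stage groups: one each for surgical stage IB to IIB, surgical stage III and stage IV, and two for non-surgical stage III.

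Section 6.2.1 gives each test "a 2-sided type I error of 0.017 (adjusted for up to 3 tests for all patients", and explains the divisor: "Patients will be included in up to 3 individual analyses". The patient who enters three is the non-surgical stage III patient (smoking cessation, nodal staging, concurrent chemoradiation). The 0.017 is then held fixed for every test. The null starts at 50%, but "This estimate for the null hypothesis will be modified using the results obtained prior to use of the decision aid".

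Section 6.3.1 says the main aim is to find out whether there is "a statistically discernible effect for the decision aid in influencing practice patterns". Section 1.3 adds, as background: "If successful, this decision aid will be disseminated more broadly to community settings". It also says that the pre/post design is there to estimate the size of the effect. Section 6.3.2 ranks "Observed effect sizes and their precision" above p-values.

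**The concern.** Six tests share the primary role, yet the adjustment divides by three. Section 6.3.1 poses what reads as a single question, and section 1.3 attaches what reads as a single decision, wider dissemination. No section states which patterns, or how many, must improve, sets an order of testing, or defines a pooled test. Logistic regression appears in 6.3.1 only for more detailed analysis.

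If the aid were declared successful because one pattern out of six crossed 0.017, the chance of a false declaration would exceed the 5% that the divisor of three suggests. Choosing the success rule after seeing six results would make this worse. What would be at stake is a decision to take the aid into community clinics on the strength of one chance finding.

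**Working it through.** **Inputs.** Six tests (2.1, 6.1.1); two-sided 0.017 per test, at most three tests per patient, one-sample exact binomial test, and the worked examples (all 6.2.1). The pre-intervention rate is treated as fixed, as 6.2.1 does. Independence between tests, and the same n for all six, are assumptions made here.

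**The plan's own figures.** 0.05/3 = 0.0167, rounded to 0.017. With 0.0085 in each tail:

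| n | null to alternative | power stated | power recomputed | attained two-sided size | upper tail only |
|---|---|---|---|---|---|
| 53 | 50% to 75% | 90% | 90.8% | 0.0127 | 0.0063 |
| 70 | 40% to 60% | 80% | 80.4% | 0.0099 | 0.0056 |
| 88 | 40% to 60% | 91% | 91.4% | 0.0121 | 0.0075 |
| 32 | 60% to 90% | 92% | 90.6% | 0.0112 | 0.0028 |
| 135 | 60% to 75% | 90% | 90.8% | 0.0138 | 0.0080 |

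The stated figures reproduce to within two points. At the full sample of 250 with a 60% null, the attained size is 0.0141 (upper tail 0.0079).

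**Error within the patient group that enters three tests.** 1 − (1 − 0.017)^3 = 5.0%. The adjustment does what it says it does.

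**Error if any one of six counted as overall success, either direction.**
- Nominal, independent: 1 − (1 − 0.017)^6 = 9.8%. Ceiling under any dependence: 6 × 0.017 = 10.2%.
- Attained, 1 − (1 − size)^6: 5.8% (n=70), 6.5% (n=32), 7.0% (n=88), 7.4% (n=53), 8.0% (n=135), 8.2% (n=250).
- A simulation in which tests sharing patients were correlated, over assumed correlations from 1 down to 0, gave 7.5% to 9.8% at the nominal level.

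**The same, counting improvements only.** Dissemination would follow an improvement, not a worsening.
- Nominal: 1 − (1 − 0.0085)^6 = 5.0%. For three tests: 1 − (1 − 0.0085)^3 = 2.5%, the directional benchmark that matches a two-sided 5%.
- Attained: 1.7% (n=32), 3.3% (n=70), 3.7% (n=53), 4.4% (n=88), 4.7% (n=135 and n=250). All are below 5%; all but n=32 are above 2.5%.

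**What strict control across six would cost.** 0.05/6 = 0.0083 per test, which is also the first step of Holm's procedure. Power becomes 84.9% (n=53), 73.1% (n=70), 87.5% (n=88), 82.8% (n=135) and 90.6% (n=32). The n=70 example falls below the 80% floor in 6.2.1.

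**What a count rule would do.** Suppose at least two of six must improve at 0.017. With a fixed null and q = 0.0085, the error is 1 − (1 − q)^6 − 6q(1 − q)^5 = 0.1% if independent, and at most 6q/2 = 2.6% under any dependence. At the n=70 power of 80.4%, the rule is met 65% of the time when two patterns truly improve, and about 2% of the time when only one does. It therefore also redefines what counts as success.

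**The case for a change.** The strongest case for acting is that 6.3.1 makes statistical discernibility the main aim, that 6.2.1 sizes the study by tests and not by interval width, and that the sentence ranking effect sizes above p-values stands under the secondary-analysis heading. A few sentences fixing the overall rule before post-intervention data are seen would cost nothing in alpha or sample size, and would stop success being defined after the fact.

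Part of this stands. The plan does not say whether the six patterns are separate questions or jointly support one claim, and the any-one-of-six reading does exceed its benchmark in nearly every setting. That reading, however, is not in the plan:
- The success sentence in 1.3 is background. It is not tied to the six tests, and the same section lists acceptability and feasibility beside effectiveness.
- Section 6.2.1 sets up a test for each stage group plus one for the whole sample, with an openly stated per-patient basis for the adjustment and no claim of study-wide control.
- Sections 1.3 and 6.1.1 point to larger evaluations later.

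Nor is there one obvious repair. Holm across six costs power. A two-of-six rule is a new definition of success, and could be met by two tests in the same non-surgical stage III patients. Reasonable statisticians would choose differently among these, or choose none.

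Replacing the 50% null by an estimate from Months 1 to 8 also raises error rates, but that comes from treating an estimate as known and not from the number of tests. With 53 baseline patients per test (an assumed figure; the plan gives none), 53 post-intervention patients and a true rate of 50%, three tests alone would already give about 20%. It is a separate matter and adds no weight here.

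**Conclusion.** The concern does not call for a change. The 0.017 is correctly computed for its stated purpose and holds 5.0% within the patient group that enters three tests. What is absent is a written step from six results to one conclusion, and the sensible default is already implied by 6.2.1: report each pattern for its own patient group with its estimate and 95% confidence interval, and rest no overall claim on a single positive test.

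The size of the issue, if that default were ignored, is 9.8% two-sided nominal (5.8% to 8.2% attained), or 5.0% nominal (1.7% to 4.7% attained) counting improvements only, against 2.5%. These figures assume a fixed pre-intervention rate and independent tests; the attained figures also assume the same n for all six. A reader of the results should give little weight to an overall claim built on one pattern out of six, but that is a caution for interpretation and not a defect in the design.
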